Cover letter

Title: Value of contralateral testicular hypertrophy in predicting the status of the intra-abdominal testis?

Running title: contralateral testicular hypertrophy in intra-abdominal testis

Category of the manuscript: Research article

Serial N: 0305079

Document Date: March 19, 2021

I have the honor to submit this original research article entitled "**Does the contralateral testicular volume decide the need for diagnostic laparoscopy in cases of unilateral impalpable undescended testis?**" for clinical registration aiming at your helpful review and hopefully your acceptance for registration.

This manuscript has not been published and is not under consideration for publication elsewhere. The investigators have no conflicts of interest to disclose and this manuscript has not received any financial funds. All of the co-authors, as well as the Alexandria University Scientific Committee, approved its publication and informed consent was signed by the parents explaining the study.

Thank you for your consideration! Waiting for your respectable reply.

Abstract

Background: This study aimed at the evaluation of the value of the estimated volume of a normal testis to predict the status of its contralateral impalpable side and hence decide the importance of laparoscopic exploration.

Methods: Participants with unilateral impalpable maldescended testis – as confirmed by clinical and sonographic examination- were enrolled in this prospective interventional study between November 2018 and August 2022 at Elshatby University Hospital, Faculty of Medicine, Alexandria University. The volume and three-dimensional diameter of the normal contralateral testis were measured by the pre-operative US using the formula: Volume = $L \times W \times H \times \pi/6$, where L is the length, W is the width, H is the height, and was correlated with the intra-operative laparoscopic findings.

Keywords: Impalpable testis; volume; ultrasound

Background

Maldescended testis or cryptorchidism is considered the most common congenital genito-urinary abnormality faced in male neonates with an incidence of 3% in full-term babies and increasing up to 30% in preterm males. However, this incidence declines to about 1% by the age of 3 months as it descends to its normal position in about 80% of cases.^{1,2}

Only 20 % of maldescended testis is impalpable being either vanishing due to an intra-uterine accident, agenetic, intra-abdominal, or inguinal with different degrees of dysplasia and atrophy.³

The gold standard method for a definitive diagnosis and management of impalpable maldescended testis is laparoscopy and according to its findings; the procedure is planned whether nothing in case of vanishing or agenetic testis, inguinal exploration in case of passing through the DIR or traction, Fowler-Stevens (FS) or one stage laparoscopic assisted orchiopexy in case of the intra-abdominal testis.^{3,4}

The size of the contralateral testis has been used to predict the condition of its contralateral impalpable one while being explored by laparoscopy by many researchers.⁵ Ultrasound (US) is considered by many surgeons as being an accurate, reproducible, and objective in situ tool for the assessment of testicular dimensions and volume.⁶

This study aimed at the assessment of the ability of the three dimensional size as well as the volume of a normal testis as measured by ultrasonography in predicting the status of its contralateral impalpable counterpart and hence deciding the need for proceeding to laparoscopic exploration of this impalpable maldescended testis.

Methods

This prospective interventional study included children with unilateral impalpable maldescended testis presented to Elshatby University Hospital, Faculty of Medicine, Alexandria University from November 2018 to August 2022. Participants with bilateral impalpable maldescended testis and those with post-operative ascended testis were excluded from the study.

After approval of the ethics committee of Alexandria Faculty of Medicine, informed consent was obtained from all parents and legal guardians of the children included in the study. Careful collection of the demographic data of all of the studied participants was followed by careful clinical examination. US abdomen, pelvis, and the inguino-scrotal region performed by the same sonographer were done for:

1. Assessment of the three-dimension diameters as well as the volume of the normal-sided testis. It is measured by the formula: Volume= $L \times W \times H \times \pi/6$, where L is the length, W is the width, and H is the height.
2. Searching for the impalpable testis at all its suspected sites; intra-abdominal, pelvic, or in inguinoscrotal region

All of the participants were subjected to laparoscopic exploration under general anesthesia with endotracheal intubation and the following data regarding the findings of the affected impalpable side was collected:

- A.** Testicular size in millimeters
- B.** Absent testis: Blind ending vas and vessels
- C.** Present intra-abdominal testis
- D.** Testis passing through the deep inguinal ring (DIR)
- E.** Patency of the DIR on the affected side (closed or open)

The procedure which was done according to the laparoscopic findings was also documented

- A.** Absent testis: Nothing
- B.** Present intra-abdominal testis: Traction 1, Fowler Stephens or laparoscopic assisted orchiopexy
- C.** Testis passing through the deep inguinal ring (DIR): Inguinal exploration and orchiopexy or excision in case of atrophied testis

Statistical Analysis

Data were fed to the computer and analyzed using IBM SPSS software package version 20.0. (Armonk, NY: IBM Corp). The **Shapiro-Wilk** was used to verify the normality of the distribution of variables, Comparisons

between groups for non-parametric variables were assessed using the **Mann Whitney test** or **Kruskal Wallis test**. The significance of the obtained results was judged at the 5% level.

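### Does the plan need changing because it does not say whether boys whose testis is found on ultrasound are eligible?

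*Combined protocol and SAP*

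**What the plan says.** The Abstract (Methods paragraph) describes the enrolled boys as having a unilateral impalpable testis "as confirmed by clinical and sonographic examination".

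The Methods section gives the population without a sonographic condition: "This prospective interventional study included children with unilateral impalpable maldescended testis". It lists two exclusions: "Participants with bilateral impalpable maldescended testis and those with post-operative ascended testis were excluded from the study". It then describes one ultrasound session with two purposes. The first is to measure the normal testis. The second reads: "Searching for the impalpable testis at all its suspected sites; intra-abdominal, pelvic, or in inguinoscrotal region".

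The aim, at the end of the Background, is to predict the status of the impalpable side from the size of the normal testis, "hence deciding the need for proceeding to laparoscopic exploration of this impalpable maldescended testis".

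Every boy is explored: "All of the participants were subjected to laparoscopic exploration under general anesthesia". The list that follows, introduced by "the following data regarding the findings of the affected impalpable side was collected", covers testicular size, absence, intra-abdominal position, passage through the deep inguinal ring, and whether the ring is open or closed. The Statistical Analysis section plans Mann-Whitney or Kruskal-Wallis comparisons at the 5% level. It names no cut-off, no accuracy measure, and no stratum or subgroup based on the ultrasound search.

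**The concern.** A search can succeed, and the Methods do not say what happens to a boy in whom it does. Read alone, they keep him: he is not excluded, he goes to laparoscopy, and he joins the volume comparison.

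That would matter because of the aim. For absent versus present, the question is most open in boys whose testis ultrasound has not found. Boys with a located testis would nearly all be present cases, apart from ultrasound error. Including them would lower the share of absent testes and shift any predictive value taken from the study, and a reader could not tell which boys the result describes. The list of collected findings also omits the ultrasound search result, which suggests that the two groups could not be separated afterwards.

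**Working it through.** The plan gives no sample size, share absent, share located, cut-off or accuracy figure, so there is nothing of its own to reproduce. The check has three parts.

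**1. The two eligibility statements side by side.** Palpation alone establishes that a testis is impalpable. Requiring sonographic confirmation adds something only if the ultrasound result bears on entry, most naturally by failing to show the testis. The Methods are silent on this; they do not say that a located testis is acceptable. A detail given in the Abstract and not repeated in the Methods is not a contradiction. On this reading no located boy is enrolled and the search result has been used, as an entry condition.

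**2. Is the search result shown to be unrecorded?** The list of findings is tied to laparoscopy. Contralateral volume, the main predictor, is not on that list either, yet it is plainly recorded. Absence from the list therefore says nothing about whether the search result was kept.

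**3. What if located boys were enrolled?** Every input here is an assumption:

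- p = share absent among all boys, 0.3 to 0.5
- v = share of present testes that ultrasound locates, 0.2 or 0.5
- sensitivity/specificity of a volume cut-off for absence: 60/80, 70/85, 85/70 or 80/90%, the same in located and not-located boys
- ultrasound never locates an absent testis

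Share absent among boys not located = p / [p + (1 − p)(1 − v)]. At p = 0.4:

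- v = 0.2: 0.4 / (0.4 + 0.6 × 0.8) = 0.4 / 0.88 = 0.455
- v = 0.5: 0.4 / (0.4 + 0.6 × 0.5) = 0.4 / 0.70 = 0.571

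Predictive values by Bayes' rule at 70/85 and p = 0.4:

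| Boys | PPV for absence | NPV |
|---|---|---|
| All pooled | 0.28 / (0.28 + 0.09) = 0.757 | 0.51 / (0.51 + 0.12) = 0.810 |
| Not located, v = 0.2 | 0.795 | 0.773 |
| Not located, v = 0.5 | 0.862 | 0.680 |

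Over the whole grid, pooling understates PPV by 2.0 to 5.4 points and overstates NPV by 1.9 to 5.1 at v = 0.2. At v = 0.5 the figures are 5.2 to 16.0 and 7.1 to 16.7. At v = 0 both are zero.

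The planned tests compare ranks, so the relevant quantity is the chance that a boy with an absent testis has the larger contralateral volume. Take normal volumes, with the absent group an assumed 0.8 SD above not-located present boys:

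- Not located only: Φ(0.8 / √2) = 0.714
- Pooled: (1 − v) × 0.714 + v × Φ((0.8 + d) / √2), where d is how many SD smaller the volume is in located than in not-located present boys
- d = 0: 0.714, whatever the value of v
- d = +0.4: 0.732 (v = 0.2), 0.758 (v = 0.5)
- d = −0.4: 0.694 (v = 0.2), 0.663 (v = 0.5)

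The rank comparison moves only if d is not zero, and nothing in the documents suggests its size or sign.

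Restricting the main comparison to not-located boys has a cost. The retained share is p + (1 − p)(1 − v), which at p = 0.4 is 88% (v = 0.2) or 70% (v = 0.5). Intervals for specificity widen by 1/√(1 − v), about 12% or 41%.

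**The case for a change.** The strongest case for a change is that the Methods, not the Abstract, are where eligibility should be settled. They drop the sonographic condition, describe the search as a step in children already included, and omit a located testis from the exclusions. The Abstract never says that the testis was not seen. The Background counts inguinal testes among the impalpable ones, and laparoscopy records testes passing through the deep ring, so impalpability alone does not rule out a testis where ultrasound looks. The study is meant to inform whether an operation under general anaesthesia is needed, so its population should be beyond doubt, and one sentence would settle it.

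Most of this stands as a comment on drafting: the documents do not define sonographic confirmation, and a looser reading is possible. It does not show that any located boy was enrolled or that a planned result would be wrong. The larger figures, up to 16.7 points, belong to predictive values that the plan does not calculate, and the understated PPV is in the cautious direction for omitting laparoscopy. The absence of an accuracy analysis is a separate matter and should not lend its weight to this one.

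Nor is the restricted analysis clearly better. The aim is to predict status, and laparoscopy records position and size as well as absence. Located boys remain informative for those, and dropping them from the main comparison costs precision.

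**Conclusion.** No change to the plan follows. The eligibility wording is incomplete, but the natural reading of the Abstract fills the gap, and on that reading the effect is exactly zero. If located boys were enrolled, the planned rank comparisons are still unaffected provided contralateral volume is the same in located and not-located boys with a testis present. An assumed 0.4 SD difference would move the underlying probability from 0.714 to between 0.663 and 0.758, in an unknown direction. The shifts in PPV and NPV rest wholly on assumed inputs and concern quantities outside the planned analysis.

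An analyst describing the cohort would ordinarily state whether the affected testis was seen on ultrasound, and could show the comparison in not-located boys beside the overall one if both kinds were enrolled. That is normal reporting and needs no amendment. The conclusion would weaken if a substantial share of enrolled boys had a located testis and predictive values were reported as the main result; the documents establish neither.

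### With no numeric age limit and no age adjustment, the (inferred) comparison of raw contralateral volume between laparoscopic groups loses power if volume varies with age; the size is unknown

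*Combined protocol and SAP*

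**What the plan says.** On eligibility, the Methods section states: "This prospective interventional study included children with unilateral impalpable maldescended testis". The only exclusions are these: "Participants with bilateral impalpable maldescended testis and those with post-operative ascended testis were excluded from the study". Neither sets an age limit, and no age strata appear elsewhere.

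The predictor is described as "Assessment of the three-dimension diameters as well as the volume of the normal-sided testis", with volume from the ellipsoid formula L × W × H × π/6. No age reference, z-score or ratio is defined. The Abstract says that this measurement "was correlated with the intra-operative laparoscopic findings". The findings recorded at laparoscopy include absent testis, intra-abdominal testis and "Testis passing through the deep inguinal ring (DIR").

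The Statistical Analysis section names Shapiro-Wilk for normality and Mann-Whitney or Kruskal-Wallis for comparisons, at the 5% level. It does not say which variables or groups are compared. That volume is compared between laparoscopic groups is inferred from the Abstract and from the aim at the end of the Background, which speaks of predicting status and "hence deciding the need for proceeding to laparoscopic exploration of this impalpable maldescended testis".

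On baseline data: "Careful collection of the demographic data of all of the studied participants was followed by careful clinical examination". Age is not named, and no use of these data in the analysis is described.

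**The concern.** If testicular volume varies with age in the boys enrolled, part of the spread in raw volume is age and has nothing to do with the opposite side. Two consequences follow, each conditional.

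- **Ages balanced between groups.** Type I error stays near 5%, but the extra spread lowers power. A predictor that separates the groups well among boys of the same age can look weak.
- **Ages different between groups.** The raw test can be significant although volume at a given age is the same in every group. Age could equally hide a real difference.

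The study is meant to inform whether a child needs laparoscopy. A finding that depends on the age mix of one hospital's series would be hard to apply to boys of other ages.

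**Working it through.** The plan gives no sample size, effect size, SD or power, so there is no figure of its own to reproduce. Every numerical input below is assumed, except the 5% level, which is the plan's (taken as two-sided).

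**Model.** log-volume = ln(1.4) × absent + s × f(age) + error. The within-age error SD is 0.35. The age term f is standardised to SD 1, and s (the age-driven SD) is 0.10, 0.35 or 0.70. Two age curves were tried: linear, and flat then rising. Groups are 20 absent and 30 present.

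**Hand check, linear curve, ages balanced.** ln(1.4) = 0.3365. Raw SD = √(0.35² + s²). Standard error factor = √(1/20 + 1/30) = 0.2887. Approximate power = Φ(0.3365 / (raw SD × 0.2887) − 1.96).

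| s | Age share of variance, s²/(0.35² + s²) | Raw SD | Approximate power, unadjusted |
|---|---|---|---|
| 0 | 0% | 0.350 | Φ(3.330 − 1.96) = 92% |
| 0.10 | 7.5% | 0.364 | Φ(3.202 − 1.96) = 89% |
| 0.35 | 50% | 0.495 | Φ(2.355 − 1.96) = 65% |
| 0.70 | 80% | 0.783 | Φ(1.489 − 1.96) = 32% |

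The normal approximation runs slightly high at this size, but it shows the pattern.

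**Simulated power, 20 versus 30, ages balanced** (10,000 runs per cell; s = 0.10 / 0.35 / 0.70).

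| Analysis | Linear curve | Flat then rising |
|---|---|---|
| Mann-Whitney on raw volume | 86 / 60 / 29% | 86 / 69 / 55% |
| Linear model, one age term | 90 / 90 / 90% | 89 / 77 / 51% |
| Linear model, age + age squared | 89 / 89 / 89% | 89 / 87 / 81% |

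With no enlargement and balanced ages, Mann-Whitney rejects in 4.4–5.2% of runs and the age + age squared model in 4.6–5.4%, so the power figures compare tests of about the same size.

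**Separating test type from age.** Mann-Whitney and the linear model differ in two ways: rank versus parametric, and unadjusted versus adjusted. A further run on the linear curve added an unadjusted t-test on log-volume.

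- s = 0.10: Mann-Whitney 85.9%, t-test 88.5%, age-adjusted model 88.6%. Nearly all of the 3-point gap is test type.
- s = 0.35: 60.1%, 63.5%, 89.2%. Of the 29 points, about 3 are test type and about 26 are age.

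**Three groups** (assumed 20 absent, 18 intra-abdominal, 12 through the deep inguinal ring (DIR); enlargement in absent only; 4,000 runs). Kruskal-Wallis power is 75 / 50 / 22% linear and 77 / 59 / 44% flat then rising. The F-test adjusted for age and age squared gives 80 / 83 / 80% and 81 / 79 / 71%.

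**Age gap of 0.5 SD, no enlargement at a given age.** Mann-Whitney at 20 versus 30 rejects in 7 / 22 / 30% of runs (linear) and 7 / 14 / 20% (flat then rising). The age + age squared model stays at 4.6–5.3%.

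**The case against.** The strongest objection is that the harm rests on facts that the documents do not supply: no age distribution, no SD, no sample size, and no statement that volume changes with age. The worst figures come from s = 0.70, where age accounts for 80% of within-group variance, and nothing in the plan anchors that value. At s = 0.10 the loss is negligible. This stands, and it is why the size is left open. It does not remove the point, because a plan with no stated age range cannot show that it lies at the harmless end.

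A second objection is that the aim is prediction from volume as measured, so an age-driven difference is not strictly a false positive. This also stands. "Value of contralateral testicular hypertrophy in predicting the status of the intra-abdominal testis" is the title, but hypertrophy appears only there and in the running title and is never defined; taking it to mean large for age is an interpretation. For prediction, an age gap mainly affects interpretation and transfer.

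A reader might go further and infer that the comparison is confounded by age, that its type I error is inflated, or that age was not recorded. The documents support none of these. They neither show nor exclude an age gap. With balanced ages the rank tests hold about 5%. Age is likely to be among the demographic data, although it is not named. Nor does the point extend to a faulty cut-off or ROC analysis, because none is planned.

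**Conclusion.** The point holds as a conditional one and should be fixed. No numeric age limit is stated, the predictor is raw, and the named comparison tests cannot take age into account. If volume varies with age in the enrolled boys, the inferred group comparison gives up power that an age-adjusted model would recover.

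Under the assumed inputs at 20 versus 30, the loss against the age + age squared model is negligible at an age-driven SD of 0.10. At 0.35 it is about 29 points on the linear curve (89 − 60) and 18 on the flat-then-rising curve (87 − 69). At 0.70 it is 60 (89 − 29) and 26 (81 − 55). Where the study would fall in that range cannot be known from the documents. The age-gap consequence is secondary and needs an imbalance that nobody has shown. Confidence is medium.

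**What to change.** 1. State the enrolled age range, and confirm that age at ultrasound is recorded for every boy.
2. Pre-specify one primary analysis: a linear model of log contralateral volume on laparoscopic group (absent, intra-abdominal, through DIR), with age and age squared. Fix both age terms in advance rather than choosing them from a plot. A single linear term is not enough if the relation bends: at s = 0.70 on the flat-then-rising curve it gives 51% power, against 55% for the raw test and 81% with age squared.
3. Keep the raw Mann-Whitney or Kruskal-Wallis tests as supportive only. If the raw test, a linear model and a logistic model were all reported with no primary named, the chance of at least one significant result with no true difference was 7–10% at 20 versus 30.
4. Make any logistic model of absent versus present secondary, use the same age terms, and state where testes passing through the DIR are assigned. Its likelihood-ratio test ran slightly high in simulation (5.7–6.6% at 20 versus 30).

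The cost is analysis wording and one stated age range. The downsides are two extra model terms (age squared costs under 1 point of power when the true relation is linear), a result less simple than one value in mL, and the need to add age at ultrasound if it is not already among the demographic data.

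### Does the lack of a fixed scan order, masking and an analysis by ultrasound search result bias the link between testicular volume and laparoscopic status?

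*Combined protocol and SAP*

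**What the plan says.** The Methods describe a single ultrasound session: "US abdomen, pelvis, and the inguino-scrotal region performed by the same sonographer were done for" two numbered purposes. The first is the three diameters and the volume of the normal testis. The second is "Searching for the impalpable testis at all its suspected sites; intra-abdominal, pelvic, or in inguinoscrotal region". Neither the Methods nor the Statistical Analysis section states a required order, a rule for locking the diameters, or a masking rule.

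The Abstract describes the boys' impalpable status "as confirmed by clinical and sonographic examination". It places the ultrasound before the operation and says that the volume "was correlated with the intra-operative laparoscopic findings".

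Under the Methods every participant has laparoscopy. The items recorded include "Testicular size in millimeters" and "Absent testis: Blind ending vas and vessels", along with intra-abdominal position, passage through the deep ring and patency of the ring.

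The Statistical Analysis section says that comparisons "between groups for non-parametric variables were assessed using the" Mann-Whitney or Kruskal-Wallis test, at the 5% level. It contains no comparison stratified or restricted by ultrasound search result.

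**The concern.** The study asks whether contralateral volume predicts the state of the impalpable side well enough to decide on laparoscopy. The ultrasound search is a direct look at that same state. A sonographer who has just failed to find a testis, and who knows the hypertrophy hypothesis in the title, might place the callipers a little wider. If so, the error would run with the outcome group and would not act as random noise. Volume is a product of three diameters, so a small shift in each is roughly tripled.

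A second, weaker route runs the other way: a surgeon who knows the volume might be swayed on operative items that need judgement.

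At stake is the main association between volume and laparoscopic status. Fixing the order of measurement and search, masking the operative recorder, and repeating the comparison among boys with no testis seen look like inexpensive protection.

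**Working it through.** The plan gives no figure to reproduce on this point: no sample size, effect, standard deviation or measurement error. The check is mainly a reading of the text, with some illustrative arithmetic.

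**1. What each route needs.**

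| Route | Must be true | What the documents show |
|---|---|---|
| Search result to measured volume | Search preceded measurement; results differed between boys; the reading shifted with the result | Measurement is listed first; sonographic confirmation may mean no testis was seen in any boy; nothing bears on a shift |
| Volume to operative record | Recorder knew the volume; the item depends on judgement | Access is not stated; absence is defined by blind-ending vas and vessels; testicular size is recorded in millimetres |
| Operative result to measured volume | Sonographer knew the operative result | Closed: the ultrasound is pre-operative |
| Ultrasound deciding who is verified | Laparoscopy depended on the scan | Closed among enrolled boys: all had laparoscopy |

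On the first route the text is open. The Abstract can be read as no testis seen in any boy. The exclusions in the Methods (bilateral impalpable testes, post-operative ascent) do not mention a testis seen on ultrasound.

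**2. How far a reading shift would carry, if there were one.** With a common relative error e in each diameter, volume is multiplied by (1+e)³. The values of e are assumed.
- e = 2%: 1.02³ = 1.061, so +6.1%
- e = 5%: 1.05³ = 1.158, so +15.8%
- e = 10%: 1.10³ = 1.331, so +33.1%

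This shows sensitivity only. It is not evidence that a shift occurred.

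**3. What restriction to boys with no testis seen would deliver.** Suppose a reading is multiplied by k whenever no testis is seen, and let A and P be the true mean volumes with absent and present testis. Within the restricted group:
- ratio: kA/kP = A/P, unchanged
- difference: kA − kP = k(A − P), rescaled by k
- a volume cut-off c becomes kc

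A shift common to the group therefore creates no difference where none exists, and it leaves rank tests unchanged. It can still move absolute differences and cut-offs, and the restricted comparison would not reveal that. The restriction also keeps only present testes that ultrasound missed, so a changed result could come from case mix alone.

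**4. Its cost in precision.** Let r be the ratio of present to absent boys and q the fraction of present boys with a testis seen, who are dropped. Assume equal variances and no absent boy reported as seen. For a two-group mean difference:

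SE ratio = √[(1 + 1/(r(1−q))) / (1 + 1/r)]

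| r | q = 0.25 | q = 0.50 | q = 0.75 |
|---|---|---|---|
| 0.5 | 1.106 | 1.291 | 1.732 |
| 1 | 1.080 | 1.225 | 1.581 |
| 2 | 1.054 | 1.155 | 1.414 |

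Example: r = 0.5, q = 0.75 gives √(9/3) = 1.732. The standard error grows by 5–11%, 15–29% or 41–73% for the three values of q. Both r and q are assumed, since the documents give neither. The planned tests are rank tests, possibly on more than two groups, so this is a guide only.

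**5. How much enrolment a procedural rule could reach.** The cover letter carries "Document Date: March 19, 2021" and enrolment is stated to run to August 2022. From 19 March 2021 to 31 August 2022 is 530 days, about 17.4 months. That is calendar time. The text is in the past tense and gives no accrual, so the number of boys affected is unknown.

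**The case for a change.** The best case for acting is that the omissions are real and inexpensive to repair. The search looks for the very state that volume is meant to predict, the expected direction was known beforehand, and the exclusions do not rule out a boy whose testis was seen. A sentence on eligibility and a statement of scan order would be possible even with enrolment complete. If search results were kept, the restricted comparison could cover boys already enrolled.

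The factual part stands: no order, no masking rule and no analysis by search result can be found, and the meaning of sonographic confirmation is unsettled. What does not stand is the step from an unstated detail to a flawed plan. The clarifying sentence and the statement of scan order describe what was done; they would not alter the design or the analysis. The restricted comparison depends on search results that both varied and were retained, and neither is documented. Even then it could not show that bias had occurred. Locking the diameters first helps only boys not yet scanned. Masking the operative recorder would be partial, because clinical examination may already reveal contralateral size, and it would protect items that are peripheral to absent or present status. The use of one sonographer also has a benefit: it removes between-operator variation from the measurement.

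**Conclusion.** No change to the plan is needed. Followed as written, it is not shown to give a wrong or worse answer. The main route requires varied search results, a search made before the measurement and a reading that moved with the result; the documents establish none of these. The lesser route hardly touches the anatomical classification of absence. Pre-operative timing and laparoscopy in every boy close the more serious routes by which the reference result could contaminate the volume or the scan could select who is verified.

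The size of any bias is unknown. It is nil on the first route if no testis was seen in any boy. If results did vary, a bias is possible but neither its size nor its direction can be derived, and the suggested sensitivity analysis would be non-diagnostic and less precise. This conclusion rests on taking the listed order as the natural working order and on the anatomical definition of absence being applied as written. What sonographic confirmation meant, the scan order used and who had seen the volume are matters that the investigators can state when reporting.
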